2 LIST OF ABBREVIATIONS

AR: Adverse Drug Reaction

AE: Adverse Event

EU: European Union

MAH: Marketing Authorization Holder

PRAC: Pharmacovigilance Risk Assessment Committee

SIP: Safety Information Packet

3 RESPONSIBLE PARTIES

Different entities from the MAH organization will be involved in the study:

[figure not shown]
- The pharmacoepidemiology unit of Global Pharmacovigilance and Epidemiology will be in charge of protocol and reports preparation
- A multidisciplinary research team made of representatives of safety Surveillance and Risk Management, Medical Affairs, Regulatory, Clinical Division will be in charge of study documents review
- The system support unit of Global Pharmacovigilance and Epidemiology will be in charge of data extraction from the pharmacovigilance database
- The Clinical Specialty Laboratory group will be in charge of data extraction from the Clinical Specialty Laboratory database
- The biostatistics group from the clinical division will be in charge of data linkage and data analysis.

4 SYNOPSIS

Title

Prevalence of immunology testing in patients treated with alglucosidase alfa with significant hypersensitivity/anaphylactic reactions

Version 3.0

As part of its assessment, PRAC requested revision of the safety information packet (SIP) to improve readability and contents and to assess effectiveness of the revised material in terms of evaluation of the process and evaluation of the outcomes.

This study is focused on evaluation of the outcomes, through the evaluation of the percentage of immunology testing in patients experiencing significant hypersensitivity/anaphylactic reactions.

Research question and objectives

This study aims to determine the prevalence of patients treated with alglucosidase alfa with significant hypersensitivity/anaphylactic reactions who undergo immunology testing. The difference in prevalence of testing between the two periods of 3 years before and after the implementation of the revised SIP (version 8.2) will be assessed as a measure of effectiveness of risk minimization measures.

Study design

Cross-sectional study; repeated analyses will be done pre- and post-implementation of the revised SIP using pre-existing data.

Population

 This study will be conducted using existing data sources recording both cases of significant hypersensitivity/anaphylactic reactions in the Genzyme's Pharmacovigilance adverse event database and routine performance of immunology testing in the Genzyme Clinical Specialty Laboratory database since treatment start.

The following population will be considered:

- All patients treated with alglucosidase alfa with a spontaneously reported significant hypersensitivity/anaphylactic reaction during the study period in countries in Europe.

Variables

The outcome will be the history of any immunology testing since treatment start as well as subtypes of testing performed in patients with a reported significant hypersensitivity/anaphylactic reaction:

- alglucosidase alfa IgE antibody
- complement activation
- serum tryptase
- alglucosidase alfa IgG antibody

Data sources

The following data sources will be considered:

- Genzyme's Pharmacovigilance adverse event database,
- Genzyme Clinical Specialty Laboratory database (capturing records and results of immunology testing conducted in these laboratories).

Reports pertaining to the same patients will be linked across databases using date of birth, initials and country of origin.

Study size

All patients available in the study population will be considered for the analysis. No assumption will be made on the expected number of patients.

Data analysis

The primary analysis population will be patients with spontaneously reported significant hypersensitivity/anaphylactic reaction while treated with alglucosidase alfa treatment course in countries in Europe. The analyses will be descriptive and will be made on all patients available in the databases at time of each analysis.

The prevalence of testing will be provided for each period (3-year period before and 3-year period after implementation of the revised SIP). The difference in prevalence rate between two groups will be calculated, with corresponding 95% confidence interval calculated based on normal approximation of two proportions.

The results will be displayed by 3-year period before and after the implementation of revised SIP and by age, gender and country in Europe when appropriate.

Milestones

Annual analyses will be conducted over a 3-year period starting one year after implementation of the revised SIP in Europe. The implementation of the revised SIP may be started from 01 September 2015 after completion of pre-updated SIP data collection.

The first report will be prepared in December 2016, based on data gathered up to one year after implementation of the revised SIP (from 01 October 2015 to 30 September 2016) and will also include results for the 3-year period before implementation of the revised SIP (from 01 September 2012 to 31 August 2015).

The second report prepared in December 2017 will add data gathered in the second year after implementation of the revised SIP (from 01 October 2016 to 30 September 2017) and the final report prepared in December 2018 will include cumulative data for both periods (from 01 September 2012 to 31 August 2015 and from 01 October 2015 to 30 September 2018).

5 AMENDMENTS AND UPDATES

None

6 MILESTONES

Table 1 summarizes the major milestones for this study.

MilestonePlanned dateRegistration in the EU PAS register3 August 2015Start of study (start of data collection)01 October 2015Interim report 1December 2016Interim report 2December 2017End of data collection30 September 2018Final report of study resultsDecember 2018

Table 1 - Major milestones for study ALGMYC07390

Table 2 summarises per country the time schedule of the distribution of the revised SIP in European countries where patients are treated with alglucosidase alfa as of the most recent update of 02 December 2015.

Table 2 - Timelines of distribution of revised SIP by country

Country	effective distribution date
Austria	pending local approval
Belgium	pending local approval
Bulgaria	local approval on 27-oct-2015
Croatia	pending local approval
Cyprus	pending local approval
Czech	pending local approval

Country	effective distribution date			
Denmark	07-oct-15			
Estonia	23-sept-15			
Finland	22-sept-15			
France	15-oct-15			
Germany	pending local approval			
Greece	pending local approval			
Hungary	pending local approval			
Ireland	30-sept-15			
Italy	pending local approval			
Netherlands	completed			
Poland	14-oct-15			
Portugal	pending local approval			
Romania	30-sept-15			
Slovenia	pending local approval			
Spain	pending local approval			
Sweden	09-oct-15			
UK	30-sept-15			
Latvia	14-sept-15			
Norway	14-oct-15			

7 RATIONALE AND BACKGROUND

As part of its assessment, PRAC requested revision of the SIP to improve readability and contents and to assess effectiveness of the revised material in terms of evaluation of the process and evaluation of the outcomes.

This study is focused on evaluation of the outcomes through the evaluation of the percentage of immunology testing in patients experiencing significant hypersensitivity/anaphylactic reactions.

8 RESEARCH QUESTION AND OBJECTIVES

This study aims to determine the prevalence of patients treated with alglucosidase alfa with significant hypersensitivity/anaphylactic reactions who undergo immunology testing. The difference in prevalence of testing between the two periods of 3 years before and after the implementation of the revised SIP (version 8.2) will be assessed as a measure of effectiveness of risk minimization measures.

9 RESEARCH METHODS

9.1 STUDY DESIGN

This study is a cross-sectional study with repeated analyses using pre-existing data covering two periods:

- A 3-year period pre-implementation of the revised SIP (from 01 September 2012 to 31 August 2015)
- A 3-year period post-implementation of the revised SIP (from 01 October 2015 to 30 September 2018)

The implementation of the revised SIP is defined as the date of effective distribution of the revised material in countries in Europe after local approval by competent authorities.

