9.7 DATA ANALYSIS

The analyses will be descriptive and will be made on all patients available in the databases at time of each analysis.

9.7.1 Analysis population:

The primary analysis population will be patients with spontaneously reported significant hypersensitivity/anaphylactic reaction while treated with alglucosidase alfa treatment course in countries in Europe. Patients will be divided by following two groups:

Group 1 (pre-SIP):

- Patients with hypersensitivity/anaphylactic reaction event onset date from 01 September 2012 to 31 August 2015

Group 2 (post-SIP):

 Patients with hypersensitivity/anaphylactic reaction event onset date from 01 October 2015 to 30 September 2018

9.7.2 Determination of patient status on immunology testing:

A patient in Group 1 (or 2) will be considered having undergone any immunology testing (immunology test = Yes) for the respectively period if one of the two conditions is met:

- i) a valid test result is available for at least one of the following tests from Genzyme Clinical Specialty Laboratory database
 - a. alglucosidase alfa IgE antibody,
 - b. alglucosidase alfa IgG antibody,
 - c. complement activation,
 - d. serum tryptase
- ii) the test date is after the alglucosidase alfa treatment start date through the end of the period cutoff (31 August 2015 for Group 1 and 30 September 2018 for Group 2)

Note that patients without a valid test meeting above criteria will be considered without having immunology test performed (immunology test=No). Therefore, there is no missing data for this endpoint.

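### Group 2 starts on 01 October 2015 in every country, although 13 of 25 countries had no distribution date for the revised SIP by 02 December 2015, so some reactions that precede local implementation count as post-SIP

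*Protocol*

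**What the plan says.** Protocol 9.1 defines the event that separates the two periods: "The implementation of the revised SIP is defined as the date of effective distribution of the revised material in countries in Europe". The same sentence makes prior approval by each country's competent authority a condition. Approval and distribution happen country by country, and Table 2 in section 6 tracks them that way, "as of the most recent update of 02 December 2015".

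The groups in 9.7.1 do not use those dates. Group 1 is "Patients with hypersensitivity/anaphylactic reaction event onset date from 01 September 2012 to 31 August 2015" and Group 2 is "Patients with hypersensitivity/anaphylactic reaction event onset date from 01 October 2015 to 30 September 2018", with no reference to the patient's country. The synopsis and 9.1 give the same calendar periods.

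In Table 2, twelve countries are marked "pending local approval". Bulgaria's entry is "local approval on 27-oct-2015", with no distribution date.

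Section 8 gives the contrast its purpose: the difference in prevalence of testing between the periods "will be assessed as a measure of effectiveness of risk minimization measures".

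**The concern.** The definition in 9.1 and the grouping in 9.7.1 cannot both hold for a country that distributed late. A reaction there after 01 October 2015 but before local distribution belongs, by 9.1, to the time before implementation. By 9.7.1 it is in the post-SIP group.

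The pre/post difference is the study's measure of whether the revised material worked, and it is reported to EMA each year. If Group 2 contains reactions managed before the material reached the country, a small difference may partly reflect slow local approval rather than ineffective material. The first interim report is most exposed, because it rests on the first post-SIP year alone.

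Nothing else in the protocol corrects for this. The by-country subgroups in 9.7.5 keep the same fixed dates, and the limitations in 9.9 do not mention staggered distribution. It is not a detail left open for a statistical analysis plan, since 9.7.1 already fixes the group definitions.

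**Working it through.** The protocol states no figure for this misclassification, so there is none to reproduce. The inputs are Table 2 and the dates in 9.1 and 9.7.1.

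**Step 1. Count of Table 2 (25 countries).**

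| Status on 02 December 2015 | Countries | Number |
|---|---|---|
| Distribution dated before 01 October 2015 | Latvia, Finland, Estonia, Ireland, Romania, UK | 6 |
| Marked completed, no date | Netherlands | 1 |
| Distribution dated 07 to 15 October 2015 | Denmark, Sweden, Poland, Norway, France | 5 |
| Approval only, no distribution date | Bulgaria | 1 |
| Awaiting local approval | Austria, Belgium, Croatia, Cyprus, Czech, Germany, Greece, Hungary, Italy, Portugal, Slovenia, Spain | 12 |

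The open countries number 12 + 1 = 13 of 25 (52%).

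**Step 2. The five October countries.** Their gaps after 01 October are 6, 8, 13, 13 and 14 days, 54 days in total. Against a window of 1,096 days this is negligible.

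**Step 3. Minimum gap in the 13 open countries.** From 01 October to 02 December 2015 is 62 days, reading Table 2 as showing no distribution in these countries by then.
- Full post period: 62 / 1,096 = 5.7%.
- First post-SIP year: 62 / 366 = 16.9%.

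These are shares of the time window within the open countries, not shares of Group 2.

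**Step 4. Minimum share of Group 2.** Assume equal numbers of reactions per country and a constant rate over time. Neither is in the protocol.
- Final analysis: (13 × 62 + 54) / (25 × 1,096) = 860 / 27,400 = 3.1%. The 13 open countries alone give 806 / 27,400 = 2.9%.
- Interim 1: 860 / (25 × 366) = 860 / 9,150 = 9.4%.

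**Step 5. Range if distribution came later.** Misclassified share = share of reactions in the open countries × delay / window. Assume those countries hold half of the reactions.

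| Assumed delay | Final analysis (36 months) | Interim 1 (12 months) |
|---|---|---|
| 6 months | 0.5 × 6/36 = 8.3% | 0.5 × 6/12 = 25% |
| 12 months | 0.5 × 12/36 = 16.7% | 0.5 × 12/12 = 50% |

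Both the half share and the delays are assumptions. Table 2 does not show delays of this length.

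**Step 6. From misclassified share to dilution.** Let D be the true difference and u the share of Group 2 with onset before local distribution. Let c, between 0 and 1, be the fraction of the SIP effect that such patients still receive. Then

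observed difference = D × [1 − u(1 − c)].

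Under 9.7.2 a Group 2 test counts up to 30 September 2018, so a patient whose reaction preceded distribution can still be tested after it, and c can exceed 0. The relative shrinkage is therefore u at most. For an assumed rise from 75% to 90% (D = 15 points) and u = 3.1%, the worst case c = 0 gives 15 × 0.969 = 14.5 points. At interim 1 there has been less time for later testing, so c is likely to be lower just where u is higher.

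**The case against.** The strongest reply is about size. The only bound that Table 2 supports is 62 days, which under equal weights turns 15 points into 14.5 at the final analysis. Table 2 is a snapshot, and the remaining countries may have distributed soon afterwards. The analyses are descriptive, with no test or success threshold; a bias toward zero cannot create a false claim of effectiveness; and by-country results are planned. All of this is fair. It does not remove the conflict between 9.1 and 9.7.1, and the planned by-country results do not help, because they use the same fixed dates. A bias toward zero also matters where the question is whether a safety measure worked.

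A second reply concerns the remedy. If late countries' pre periods are extended while 9.7.2 keeps the Group 1 test cutoff at 31 August 2015, a test prompted by a reaction after that date could not count. Group 1 prevalence would fall and the SIP effect would be inflated. If some countries contribute only to the pre period, the crude difference is also confounded by country. Both points stand, and the fix must meet them.

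A reader might infer more than the documents support:
- **The effect shrinks by the misclassified share, perhaps 8% to 50%.** Those shares rest on an assumed patient distribution and assumed delays, and the testing window in 9.7.2 makes the dilution less than proportional.
- **Most of Group 2 is unexposed, because 18 of 25 countries had not distributed on 01 October** (19 if the Netherlands was later). This counts countries, not patients, and five of the 18 followed within 6 to 14 days.
- **Leaving out September 2015 is an error.** It costs one month in 73 and misclassifies nobody.
- **Group 1 is contaminated too.** The earliest dated distribution is 14 September 2015, after Group 1 closes.

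**Conclusion.** The point holds. Group 2 as fixed in 9.7.1 does not meet the protocol's own definition of implementation in 13 of 25 countries for at least the first 62 days of the post period. The bias in the pre/post difference is toward zero, provided that patients with earlier onset are tested at a rate between the pre-SIP and post-SIP rates. It is largest in interim report 1.

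The size cannot be fixed from the protocol. The floor is 5.7% of the 36-month window and 16.9% of year one within the open countries, or about 3% of Group 2 at the final analysis under equal country weights. How far above that floor the true share lies depends on patients per country and on distribution dates after 02 December 2015, neither of which is given. The documents do not show that the study would miss a real effect. They show that its comparison is mislabelled in a way that can be removed cheaply.

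**What to change.** 1. Complete Table 2 with the actual distribution date for every country, including the Netherlands and Bulgaria, before each analysis.
2. In the synopsis, 9.1 and 9.7.1, start Group 2 in each country at that country's effective distribution date, so that no reaction before local distribution counts as post-SIP.
3. Choose one rule for the time in between. Either keep Group 1 as it is, ending 31 August 2015, and exclude reactions between then and local distribution; or extend the pre period to the local date and move the Group 1 test cutoff in 9.7.2 to the same country-specific date. The first is simpler and leaves the Group 1 cutoff unchanged.
4. In 9.7.5, compute the difference in countries that contribute to both periods, or stratify by country, so that the country mix does not drive it.
5. Report the present fixed-date split as a sensitivity analysis.

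The cost is wording and one look-up table. Event date and country are already study variables or linkage keys, and the sponsor already tracks distribution. The downside is that late countries have a post period shorter than the 3 years named in section 8, and Group 2 is somewhat smaller. Each report should state the post period by country.

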9.2 SETTING

The following data sources will be considered:

- Genzyme's Pharmacovigilance adverse event database,
- Genzyme Clinical Specialty Laboratory database (capturing records and results of immunology testing conducted in these laboratories).

Reports pertaining to the same patients will be linked across databases using date of birth, initials and country of origin.

The Genzyme's Pharmacovigilance adverse event database will be used to identify the population of interest for each study period:

• All patients with a spontaneously reported significant hypersensitivity/anaphylactic reaction occurring during alglucosidase alfa treatment course in countries in Europe.

The following criteria will be used to identify patients with a reported significant hypersensitivity/anaphylactic reaction occurring during alglucosidase alfa treatment course:

• cases identified by the Standardized MedDRA Query "Anaphylactic reaction" and "hypersensitivity".

The Genzyme Clinical Specialty Laboratory database will be used to identify the full history of immunology testing since initiation of treatment with alglucosidase alfa in patients identified from the Genzyme's Pharmacovigilance adverse event database.

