9.3 VARIABLES

The following variables will be considered for the analysis.

The characteristics of patients with a reported significant hypersensitivity /anaphylactic reaction (if available):

- age
- gender
- weight
- description of hypersensitivity/anaphylactic reactions
 - nature of event
 - outcome
 - seriousness
 - medically confirmed
 - event date
 - event severity
 - mild, moderate, severe
 - grade 1 to 5 according to NCI Common Terminology Criteria for Adverse Events
- history of hypersensitivity/ anaphylactic reactions
- history of reported drug exposure

The characteristics of alglucosidase alfa treatment course (if available):

- treatment start date
- number of doses received
- treatment dosage received

The history of immunology testing performed since treatment start:

- any immunology testing
- alglucosidase alfa IgE antibody
- complement activation
- serum tryptase
- alglucosidase alfa IgG antibody

Immunology testing results will be generally reported as titers.

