9.7.3 Demographic and baseline disease characteristics

Patient demographics and baseline disease characteristics will be summarized using descriptive statistics: number of observations (n), mean, median, standard deviation (SD), minimum, and maximum. Categorical variables will be summarized using frequencies and percentages. Denominator will be based on the number of patients in the analysis population as defined in Section 9.7.1.

Following variables will be summarized by Group (1 or 2):

- patient characteristics (age, gender, weight, country/region)
- history of hypersensitivity/anaphylactic reactions

9.7.4 Alglucosidase alfa treatment information and the details on hypersensitivity/anaphylactic reaction event

Following alglucosidase alfa treatment information will be summarized by group as well as the combined analysis population:

- time from treatment initiation to first onset of hypersensitivity/anaphylactic reactions event within the study period
- number of doses received prior to first onset of hypersensitivity/anaphylactic reactions event within the period

The details of the hypersensitivity/anaphylactic reactions event reported in each of the periods will be summarized by intensity, seriousness (SAE or not) of the event, and relationship to alglucosidase alfa treatment, respectively. The summaries will be provided by analysis group (1 and 2). For multiple events occurred in the same study period, patients will be counted only once and only the event with the worst category will be considered for the corresponding

analysis. Corresponding listing will be provided with detailed information collected in the database

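### The objective concerns significant reactions, but entry requires only a MedDRA query hit, and the crude pre/post difference is never examined by seriousness or severity

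*Protocol*

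**What the plan says.** Protocol section 8 sets the aim as the "prevalence of patients treated with alglucosidase alfa with significant hypersensitivity/anaphylactic reactions who undergo immunology testing", and uses the difference between the two three-year periods as a measure of how well risk minimisation worked. Section 9.2 gives the population as "All patients with a spontaneously reported significant hypersensitivity/anaphylactic reaction occurring during alglucosidase alfa treatment course in countries in Europe". The criterion offered for identifying these patients is a single line: "cases identified by the Standardized MedDRA Query 'Anaphylactic reaction' and 'hypersensitivity".

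Section 9.7.1 splits patients by onset date alone. Group 1, for example, is "Patients with hypersensitivity/anaphylactic reaction event onset date from 01 September 2012 to 31 August 2015"; the word significant does not appear in either group definition.

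Section 9.3 collects, if available, seriousness, medical confirmation and severity, the last both as "mild, moderate, severe" and as "grade 1 to 5 according to NCI Common Terminology Criteria for Adverse Events". Section 9.7.4 has the included events "summarized by intensity, seriousness (SAE or not) of the event, and relationship to alglucosidase alfa treatment, respectively", by group, using the worst category per patient.

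Section 9.7.5 reports the percentage tested in each group and the difference between groups, with a 95% interval from the normal approximation (exact if numbers are small). Its subgroups are age, gender and country or region. Section 9.9 discusses missing data, tests done in other laboratories and linkage, but not the mix of reported cases.

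**The concern.** Two things follow if the plan is carried out as written.

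First, the result answers a wider question than the one asked. A mild, non-serious or unrelated event that hits the query counts in the same way as a severe anaphylactic reaction.

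Second, the comparison between periods is exposed to case mix. The cases are spontaneous reports collected over about six years, and revised safety material could itself change which reactions get reported. If milder cases are tested less often, a change in the reported mix could look like an effect of the revised material or hide a real one. This difference is the study's measure of effectiveness, and no planned analysis looks at it within levels of seriousness or severity.

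**Working it through.** **1. Is there a threshold anywhere?** Sections 8, 9.2, 9.5 and 9.7.1 all refer to significant reactions, and none defines the word beyond the query rule in 9.2. Section 9.7.1 adds only onset dates. Section 9.3 lists severity from mild upwards and grades from 1 upwards as descriptive variables. Section 9.7.4 treats SAE status and relationship as things to tabulate, not as entry conditions. Section 9.2 does not say whether the two queries are joined as either or both; neither reading adds a threshold.

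**2. The plan's own figures.** Table 3 gives intervals for one prevalence. For n = 100 and 75%: 0.75 ± 1.96 × √(0.75 × 0.25 / 100) = 0.75 ± 0.085, or 66.5% to 83.5%, as printed. All 20 intervals reproduce, apart from a last-digit difference in one upper limit (n = 50, 95%: 99.2 computed, 99.1 printed). Table 3 is not in dispute. It does not address the difference between periods.

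**3. How the crude difference responds to case mix.** Let s be the share of severe (or serious) cases, and let p_sev and p_mild be the testing rates in the two strata, the same in both periods. Crude prevalence is s × p_sev + (1 − s) × p_mild, so

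crude difference = (s_post − s_pre) × (p_sev − p_mild).

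The protocol gives none of these inputs, so all values below are assumptions. For a 20-point shift in the severe share:

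| Gap in testing rate | Spurious difference |
|---|---|
| 10 points | 0.20 × 10 = 2 points |
| 20 points (90% vs 70%) | 0.20 × 20 = 4 points |
| 40 points (90% vs 50%) | 0.20 × 40 = 8 points |

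The sign follows the direction of the shift.

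**4. The 40-point case against sampling error.** With the severe share going from 30% to 50%:
- before: 0.3 × 90 + 0.7 × 50 = 62%
- after: 0.5 × 90 + 0.5 × 50 = 70%
- difference: +8 points, with no change in practice

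The interval is 8 ± 196 × √((0.62 × 0.38 + 0.70 × 0.30) / n) points:

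| Patients per period | 95% interval (points) |
|---|---|
| 50 | −10.5 to 26.5 |
| 100 | −5.1 to 21.1 |
| 200 | −1.3 to 17.3 |
| 300 | 0.4 to 15.6 |

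**5. High prevalence limits the gap.** With overall prevalence P, the largest possible gap is reached when every severe case is tested: gap = (1 − P) / (1 − s). At P = 95% and s = 50% this is 0.05 / 0.50 = 10 points, so a 20-point shift moves the difference by about 2 points at most. At P = 75% and s = 50% the ceiling is 0.25 / 0.50 = 50 points. Table 3 considers prevalences from 50% to 95%, so both situations are within the plan's own range.

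**6. Standardising removes it.** Applying one common mix, say 40% severe, to the step 4 rates gives 0.4 × (90 − 90) + 0.6 × (50 − 50) = 0.

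**The case against.** **The term does have a working definition.** Section 9.2 presents the query rule as the way to identify significant reactions. A reader might infer that the restriction is simply ignored; the text does not support that. What stands against the plan is that the rule is broader than the word, and that the protocol's own variables show the breadth.

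**Listing a scale does not forecast its use.** Sections 9.3 and 9.7.4 allow mild, non-serious and unrelated events. They do not say how many there will be, and nothing in the protocol shows that such events dominate.

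**The endpoint may weaken the severity gradient.** Section 9.7.2 counts any valid test from treatment start to the period cutoff, including IgG, and so can count tests done before the reaction. Such tests cannot be a response to its severity. This stands, and is a good reason not to treat the 40-point gap as likely.

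**A shift would be visible, and the analysis is descriptive.** The by-group tables in 9.7.4 could reveal a change in mix. They would not show what the difference would have been without it. An additional subgroup or standardised estimate could be placed in a statistical analysis plan, so its absence alone is no defect. The case definition, however, is fixed in 9.2, and a threshold added elsewhere would change the protocol's population.

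**A stricter filter is hard to build.** The safety packet is not among the documents, so it cannot be assumed to define a significant reaction. Relationship is tabulated in 9.7.4 but is not in the 9.3 variable list. Seriousness and severity come only if available, and 9.9 warns of missing data. Adjusting for seriousness, age and country together could be too sparse near 50 patients. These points stand and shape the fix.

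**Conclusion.** The mismatch between the stated population and the entry rule is established from the text and needs no assumption. The protocol will estimate testing prevalence among all query hits while describing them as significant reactions.

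The effect on the pre/post difference is conditional. It requires both a link between severity and testing and a change in the reported mix. For a 20-point shift, it is about 2 points with a 10-point gap and 8 points with a 40-point gap. A reader might infer that the planned difference is biased by some known amount, or that a spurious positive finding is likely. Neither follows: the documents give no testing rates by severity and no case mix, and in the 8-point example the interval excludes zero only at 300 per period. At smaller sizes the point estimate would still be displaced. The point deserves correction because the difference is the effectiveness measure and the remedy is cheap.

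**What to change.** 1. In 9.2, keep all query hits as the broad population, and state that it is broader than significant reactions. Say whether the two queries are joined as either or both.
2. Define a significant set in the protocol from recorded seriousness and severity or grade, with a stated category for missing values. In 9.7.5, give the prevalence and the pre/post difference in this set.
3. In 9.7.5, report the pre/post difference by seriousness, and one difference standardised on seriousness alone beside the crude one. Do not standardise jointly with age and country.

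This uses fields that section 9.3 already lists and needs no new data collection. It costs some wording, one flag and a little more analysis. The restricted set will be smaller and some fields will be missing. If it held half of 200 patients (an assumption), Table 3 at 50% prevalence shows the interval widening from 43.1–56.9% to 40.2–59.8%. Keeping the broad population in the report limits that loss.
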